7.3. Safety

Planned time points for all safety assessments are listed in the Time and Events Table (Section 7.1). Additional time points for safety tests may be added during the course of the study based on newly available data to ensure appropriate safety monitoring.

7.3.1. Adverse Events (AE) and Serious Adverse Events (SAEs)

The definitions of an AE or SAE can be found in [Appendix 5](#).

The investigator and their designees are responsible for detecting, documenting and reporting events that meet the definition of an AE or SAE.

7.3.1.1. Time period and Frequency for collecting AE and SAE information

- Any SAEs assessed as related to study participation (e.g., protocol-mandated procedures, invasive tests, or change in existing therapy) or related to a GSK product will be recorded from the time a subject consents to participate in the study up to and including any follow-up contact.
- AEs will be collected from the start of Study Treatment until the follow-up contact (see Section 7.3.1.3), at the timepoints specified in the Time and Events Table (Section 7.1).
- Medical occurrences that begin prior to the start of study treatment but after obtaining informed consent may be recorded on the Medical History/Current Medical Conditions section of the CRF.
- All SAEs will be recorded and reported to GSK within 24 hours, as indicated in [Appendix 5](#).
- Investigators are not obligated to actively seek AEs or SAEs in former study subjects. However, if the investigator learns of any SAE, including a death, at any time after a subject has been discharged from the study, and he/she considers the

event reasonably related to the study treatment or study participation, the investigator must promptly notify GSK.

NOTE: The method of recording, evaluating and assessing causality of AEs and SAEs plus procedures for completing and transmitting SAE reports to GSK are provided in [Appendix 5](#).

7.3.1.2. Method of Detecting AEs and SAEs

Care will be taken not to introduce bias when detecting AEs and/or SAEs. Open-ended and non-leading verbal questioning of the subject is the preferred method to inquire about AE occurrence. Appropriate questions include:

- “How are you feeling?”
- “Have you had any (other) medical problems since your last visit/contact?”
- “Have you taken any new medicines, other than those provided in this study, since your last visit/contact?”

7.3.1.3. Follow-up of AEs and SAEs

After the initial AE/SAE report, the investigator is required to proactively follow each subject at subsequent visits/contacts. All SAEs, and non-serious AEs of special interest (as defined in Section [4.11.1](#)) will be followed until resolution, until the condition stabilizes, until the event is otherwise explained, or until the subject is lost to follow-up (as defined in Section [5.4](#)). Further information on follow-up procedures is given in [Appendix 5](#).

7.3.1.4. Cardiovascular and Death Events

Investigators will be required to fill out event specific data collection tools for the following AEs and SAEs:

- Myocardial infarction/unstable angina
- Congestive heart failure
- Arrhythmias
- Valvulopathy
- Pulmonary hypertension
- Cerebrovascular events/stroke and transient ischemic attack
- Peripheral arterial thromboembolism
- Deep venous thrombosis/pulmonary embolism
- Revascularisation

This information should be recorded in the specific cardiovascular eCRF within one week of when the AE/SAE(s) are first reported.

7.3.1.5. Disease-Related Events and/or Disease-Related Outcomes Not Qualifying as SAEs

An event which is part of the natural course of the disease under study (i.e., disease progression or hospitalization due to disease progression) does not need to be reported as a serious adverse event (SAE). Death due to disease under study is to be recorded on the Death electronic case report form (eCRF). However, if the underlying disease (i.e., progression) is greater than that which would normally be expected for the subject, or if the investigator considers that there was a causal relationship between treatment with study treatment(s) or protocol design or procedures and the disease progression, then this must be reported as a SAE.

7.3.1.6. Regulatory Reporting Requirements for SAEs

Prompt notification by the investigator to GSK of SAEs related to study treatment (even for non- interventional post-marketing studies) is essential so that legal obligations and ethical responsibilities towards the safety of subjects and the safety of a product under clinical investigation are met.

GSK has a legal responsibility to notify both the local regulatory authority and other regulatory agencies about the safety of a product under clinical investigation. GSK will comply with country specific regulatory requirements relating to safety reporting to the regulatory authority, Institutional Review Board (IRB)/Independent Ethics Committee (IEC) and investigators.

Investigator safety reports are prepared for suspected unexpected serious adverse reactions according to local regulatory requirements and GSK policy and are forwarded to investigators as necessary.

An investigator who receives an investigator safety report describing a SAE(s) or other specific safety information (e.g., summary or listing of SAEs) from GSK will file it with the IB and will notify the IRB/IEC, if appropriate according to local requirements.

7.3.2. Pregnancy

Details of all pregnancies in female subjects or female partners of male subjects will be collected after the start of dosing and until 7 days post-last dose.

If a pregnancy is reported then the investigator should inform GSK within 2 weeks of learning of the pregnancy and should follow the procedures outlined in [Appendix 7](#).

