4.2. Treatment Schedule and Duration

Treatment with GSK2879552 in both arms will be administered orally as continuous daily dosing until progression. Azacitidine will be administered at 75 mg/m² on days 1-7 of each 28 day cycle by intravenous (iv) infusion or subcutaneous (sc) injection (route of administration: by physicians choice). Subcutaneous administration will be required during the first cycle as PK information will be collected.

Alterations to the dose and schedule of GSK2879552 may be incorporated based on emerging safety, tolerability, and PK data. The dose and schedule of azacitidine may be also altered based on emerging safety, tolerability and PK data. Azacitidine dosing on Mon-Fri (Days 1-5) and Mon-Tue (Days 8-9) may be allowed on a case by case basis.

Subjects may continue treatment in the study until disease progression, unacceptable toxicity, or withdrawal of consent. Subjects experiencing disease progression on mono therapy (Arm A) will be allowed to cross over to be treated with the combination (Arm B) once the RP2D has been established. All subjects will be followed after study treatment discontinuation until death, lost to follow-up or withdrawal of consent. The duration of the study will depend on recruitment rates, and timing of subject's duration on study. Subjects may be allowed to continue on study treatment after disease progression if the Investigator, in consultation with the sponsor's Medical Monitor, determines that continuing treatment will benefit the patient.

4.3. Part 1

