4.7. Permanent Discontinuation of Study Treatment

Subjects will receive study treatment until disease progression (according to IWG), death, withdrawal of consent, or unacceptable toxicity, including meeting stopping criteria for liver chemistry. The investigator may discuss with a GSK Medical Monitor continuing a subject who is receiving clinical benefit but has met the formal criteria for disease progression, if the following criteria are met: Investigator-determined clinical benefit (e.g. symptomatic improvement), lack of significant toxicity (no drug related non-

hematologic grade 3/4 AEs within the last 4 weeks) and no therapeutic alternatives expected to provide durable responses.

In addition, study treatment may be permanently discontinued for any of the following reasons:

- Substantial deviation(s) from the protocol
- Request of the subject or proxy (withdrawal of consent by subject or proxy)
- Investigator's discretion
- A clinically significant adverse event leading to an interruption of treatment for greater than 14 days. If the investigator and GSK Medical Monitor conclude that the benefit: risk is positive and supports continued treatment in a subject who has had a > 14 day treatment delay, then the subject may continue therapy with the approval of the GSK Medical Monitor on case by case basis.
- Persistent G4 thrombocytopenia for >4 weeks not attributed to disease or requires platelet transfusions for bleeding in the absence of the disease
- Intercurrent illness that prevents further administration of study treatment(s)
- Subject is lost to follow-up.
- Study is closed or terminated.

Once a subject has permanently discontinued study treatment, the subject will not be allowed to re-enter this study. All subjects who discontinue from study treatment will have safety assessments at the time of discontinuation and during post-study treatment monthly follow-up.

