| Renal impairment | Renal toxicity ranging from elevated serum creatinine to renal failure and death have been reported in patients treated with intravenous azacitidine in combination with other chemotherapeutic agents for nonMDS conditions. Renal tubular acidosis has been also reported in patients treated with azacitidine and etoposide. Patients with renal impairment may be at increased risk for renal toxicity. Also, azacitidine and its metabolites are primarily excreted by the kidney. | 
 - Subjects with inadequate renal function are excluded - Chemistry panel including serum creatinine, BUN and electrolytes are monitored weekly for the first 4 weeks and monthly thereafter. - Treatment stopping criteria based on serum bicarbonate, creatinine and or BUN is provided. |
| Teratogenic effect | Azacitidine caused congenital malformations in animals and may cause fetal harm when administered to a pregnant woman. In animal studies, pre-conception treatment of male mice and rats resulted in increased embryofetal loss in mated females | 
 - Pregnancy test will be performed at screening and monthly thereafter. - Female subjects with child bearing potential must have a negative serum pregnancy test within 7 days of first dose of study treatment and agree to use effective contraception, during the study and for 7 days following the last dose of study treatment. - Lactating females will be excluded. - Male subjects with a female partner of childbearing potential must have either had a prior vasectomy or agree to use effective contraception from the administration of the first dose of study treatment until 3 months after the last dose of study treatment. |

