a. Isolated bilirubin >1.5 X ULN is acceptable if bilirubin is fractionated and direct bilirubin <35% or subject has a diagnosis of Gilbert's syndrome

GENDER and REPRODUCTIVE POTENTIAL

10. Women of childbearing potential must have a negative serum pregnancy test within 7 days of first dose of study treatment and agree to use effective contraception, as defined in [Appendix 7](#) of this protocol, during the study and for 7 days following the last dose of study treatment.
11. Men with a female partner of childbearing potential must have either had a prior vasectomy or agree to use effective contraception, as defined in [Appendix 7](#) of this protocol, from the administration of the first dose of study treatment until 3 months after the last dose of study treatment to allow for clearance of any altered sperm.

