5.6. Subject and Study Completion

A subject will be considered to have completed the study if they are followed until death.

Subjects who have not died, and are no longer being followed for survival are considered to have discontinued the study. The End of Study eCRF should only be completed when a subject is no longer being followed.

The study will be considered completed for the purpose of a final analysis when 70% of subjects enrolled in Part 2 have progressed or died. If available, subjects continuing on treatment at the time of final analysis may be offered the option to continue in a rollover trial.

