12.7.2. Collection of Pregnancy Information

- Investigator will collect pregnancy information on any female subject, who becomes pregnant while participating in this study
- Information will be recorded on the appropriate form and submitted to GSK within 2 weeks of learning of a subject's pregnancy.
- Subject will be followed to determine the outcome of the pregnancy. The investigator will collect follow up information on mother and infant, which will be forwarded to GSK. Generally, follow-up will not be required for longer than 6 to 8 weeks beyond the estimated delivery date.
- Any termination of pregnancy will be reported, regardless of fetal status (presence or absence of anomalies) or indication for procedure.

- While pregnancy itself is not considered to be an AE or SAE, any pregnancy complication or elective termination of a pregnancy will be reported as an AE or SAE.
- A spontaneous abortion is always considered to be an SAE and will be reported as such.
- Any SAE occurring as a result of a post-study pregnancy which is considered reasonably related to the study treatment by the investigator will be reported to GSK as described in [Appendix 5](#). While the investigator is not obligated to actively seek this information in former study participants, he or she may learn of an SAE through spontaneous reporting.

Any female subject who becomes pregnant while participating

- will be withdrawn from the study
- Investigator will attempt to collect pregnancy information on any female partner of a male study subject who becomes pregnant while participating in this study.
- After obtaining the necessary signed informed consent from the female partner directly, the investigator will record pregnancy information on the appropriate form and submit it to GSK within 2 weeks of learning of the partner's pregnancy
- Partner will also be followed to determine the outcome of the pregnancy. Information on the status of the mother and child will be forwarded to GSK.
- Generally, follow-up will be no longer than 6 to 8 weeks following the estimated delivery date. Any termination of the pregnancy will be reported regardless of fetal status (presence or absence of anomalies) or indication for procedure.

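### Section 7.3.2 stops collecting partner pregnancies 7 days after last dose, about 12 weeks short of the 3-month period the protocol sets for male-mediated risk

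*Protocol*

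**What the plan says.** Section 7.3.2 sets one collection window for two groups. Details of pregnancies in female subjects or "female partners of male subjects will be collected after the start of dosing and until 7 days post-last dose". Its next sentence, which has no date limit, has the investigator inform the sponsor within 2 weeks of learning of a reported pregnancy and follow Appendix 7.

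The contraception rules use two periods. Inclusion criterion 10 ends the female period 7 days after last dose. Inclusion criterion 11 runs the male period from the "first dose of study treatment until 3 months after the last dose of study treatment to allow for clearance of any altered sperm". The risk table in Section 4.11.1 repeats both periods and, under azacitidine, gives the hazard for men: "pre-conception treatment of male mice and rats resulted in increased embryofetal loss in mated females".

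Appendix 7 has its own partner rule in Section 12.7.2: "Investigator will attempt to collect pregnancy information on any female partner of a male study subject who becomes pregnant while participating in this study". The protocol does not define participation for this purpose. Section 4.2 states: "All subjects will be followed after study treatment discontinuation until death, lost to follow-up or withdrawal of consent". Section 5.6 states: "Subjects who have not died, and are no longer being followed for survival are considered to have discontinued the study". Section 12.7.1 gives the male contraception period as a bracketed choice between two half-life-based options, with no number filled in.

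**The concern.** The 7-day limit suits female subjects, whose contraception period it matches. Applied to partners of male subjects, it does not match the reason the protocol gives for the longer male period. If sperm may be altered for 3 months after the last dose, a conception on day 30 or day 60 is one whose outcome the sponsor would want to know. As written, the only dated rule has closed collection by then.

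At stake is the completeness of safety information on male-mediated exposure, and whether sites have one clear instruction. Efficacy, sample size and error rates are not involved.

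**Working it through.** The plan states no figure to reproduce. The check compares the stated windows and then asks whether any other provision fills the difference.

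**Length of the gap**

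- End of partner collection (Section 7.3.2): day 7 after last dose.
- End of male contraception (inclusion criterion 11; Section 4.11.1): 3 months after last dose, taken as 90 to 92 days.
- Gap = end of male period − end of collection: 90 − 7 = 83 days; 92 − 7 = 85 days.
- At 91 days (13 weeks): 91 − 7 = 84 days, or 12 weeks. As a share of the post-treatment part of the male period, 84/91 = 92%.
- Time on treatment is fully covered, because Section 7.3.2 starts at the start of dosing. The gap is only day 8 to about day 91.

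**Does another provision cover days 8 to 91?**

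- *Section 7.3.2, second sentence.* It is undated, so a pregnancy that happens to be reported on day 30 could be read to trigger it. It governs what to do with a report. It does not say that collection goes on past day 7.
- *Section 12.7.2, partner sentence.* If participation includes survival follow-up, as Sections 4.2 and 5.6 would allow, it reaches past day 7. If participation means time on treatment, or if the dated window in Section 7.3.2 governs, it does not. The text does not settle this.
- *Section 12.7.2, post-study clause.* It covers related SAEs resulting from a post-study pregnancy, if the investigator learns of them. The pregnancy alone does not qualify: "While pregnancy itself is not considered to be an AE or SAE".
- *Section 7.3.1.1.* Related SAEs are recorded up to any follow-up contact. Its last bullet requires notification of related SAEs learned of after discharge from the study, with no duty to seek them. Both are limited to SAEs.
- *Section 4.7.* Subjects who stop treatment "will have safety assessments at the time of discontinuation and during post-study treatment monthly follow-up". Pregnancy is not named.
- *Section 7.1, footnote 16.* The 2-monthly contacts collect survival, PFS and the start of new treatment, by chart review or phone. Pregnancy is not listed.

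These routes would catch a complication, termination or abortion that met their conditions. None clearly collects an uncomplicated partner pregnancy in the gap.

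**Expected number of events**

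The documents do not say how many subjects will be men with a partner of childbearing potential. Assume 0 to 10% of the 74 planned subjects (Section 4.8), or 0 to 7 couples. Use the Appendix 7 criterion of a failure rate below 1% per year and assume compliant use:

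- Expected pregnancies = couples × yearly rate × gap in years
- Upper end: 7 × 0.01 × 84/365 = 0.016, so fewer than 0.02. Lower end: 0.

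**The case against.** The strongest reply is that nothing conflicts. Inclusion criterion 11 says how long a man uses contraception; Section 7.3.2 says how long pregnancy details are collected. A site can obey both, and nothing in the protocol requires equal periods. This stands. A reader might infer that the protocol contradicts itself or leaves partners unprotected, and neither is supported. The contraception rule is intact, and the fault is a collection window that does not follow the protocol's own stated reason for concern.

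A reader might also infer a direct conflict between Section 7.3.2 and Section 12.7.2. That holds only if participation is read to include survival follow-up. An equally ordinary reading is that Section 7.3.2 sets the dates and Appendix 7 supplies the procedures, in which case the two agree. The documents support an ambiguity and no more.

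A third inference, that nothing about a partner pregnancy could be reported after day 7, also goes too far. The undated second sentence of Section 7.3.2, the post-study SAE clause in Section 12.7.2 and the last bullet of Section 7.3.1.1 all leave some route open.

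Finally, the consequence is small. Section 2.1.2 gives a median age at MDS diagnosis of 73 years, and the expected number of events is close to zero. This limits the importance of the point but does not remove the mismatch.

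**Conclusion.** The point holds as a minor inconsistency in safety collection. The only dated window for partner pregnancies ends about 83 to 85 days before the 3-month period that the protocol sets for clearance of altered sperm. The length of the gap rests only on taking 3 months as 90 to 92 days.

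The mismatch with inclusion criterion 11 and Section 4.11.1 is clear from the text. Whether Section 12.7.2 reaches further is uncertain, because participation is undefined. Expected events are fewer than 0.02 under the assumed 0 to 7 couples and compliant contraception; non-compliance would raise that figure by an amount the documents do not allow to be estimated. No endpoint, analysis or decision rule is affected. The change is worth making when the protocol is next amended.

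**What to change.** In Section 7.3.2, keep 7 days after last dose for female subjects and set collection for female partners of male subjects to pregnancies arising up to 3 months after last dose. State the same 3 months in the partner sentence of Section 12.7.2, which removes the dependence on what participation means. In Section 12.7.1, replace the bracketed male period with 3 months, to agree with inclusion criterion 11.

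Asking men with a partner of childbearing potential about pregnancy at an existing post-treatment contact would help but is optional.

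The cost is amendment wording and a slightly longer collection period for a small number of subjects. No new visit is needed.

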7.3.3. Physical Exams

A complete physical examination will include, at a minimum, assessment of the Cardiovascular, Respiratory, Gastrointestinal and Neurological systems. Height and weight will also be measured and recorded.

A brief physical examination will include, at a minimum assessments of the skin, lungs, cardiovascular system, and abdomen (liver and spleen).

- Investigators should pay special attention to clinical signs related to previous serious illnesses

7.3.4. Vital Signs

Vital sign measurements will include systolic and diastolic blood pressure, temperature, respiration rate and heart rate. Vital signs should be measured after resting for at least 5 minutes in a semi-supine position. Vital signs will be measured more frequently if warranted by clinical condition of the subject. Refer to the SPM for details regarding measurement of vital signs.

7.3.5. Electrocardiogram (ECG)

Single 12-lead electrocardiogram (ECGs) will be obtained at designated time points during the study using an ECG machine that automatically calculates the heart rate and measures PR, QRS, QT, and corrected QT (QTc) intervals. At each assessment a 12-lead ECG will be performed by qualified personnel at the site after the subject has at least a 5 minute rest and is in a semi-recumbent or supine position.

